## 1.0 STUDY GOAL AND OBJECTIVES

The goal of the study is to evaluate the Ovation Alto Abdominal Stent Graft System in subjects with abdominal aortic aneurysm (AAA). The primary study objective is to evaluate treatment success at 12 months in patients treated with Ovation Alto relative to a performance goal of 80%.

Treatment success will be defined as:

- Technical success\*
- Freedom from type I & III endoleaks at 12 months
- Freedom from stent graft migration > 10 mm at 12 months (compared to 1-month baseline)
- Freedom from AAA enlargement > 5mm at 12 months (compared to 1-month baseline)
- Freedom from AAA rupture through 12 months
- Freedom from conversion to open repair through 12 months
- Stent graft stenosis, occlusion or kink requiring secondary intervention through 12 months
- Thromboembolic event\*\* attributable to stent graft requiring secondary intervention through 12 months
- Stent fracture requiring secondary intervention through 12 months

\*Technical Success is defined as:

- Successful delivery (i.e. ability to deliver the implant to the intended location site without the need for unanticipated corrective intervention related to delivery, using an adjunctive device outside of the Ovation Alto Abdominal Stent Graft System);
- Successful and accurate deployment, defined as:
  - deployment of the endovascular stent graft in the planned location;
  - patency of the endovascular stent graft, absence of device deformations (e.g. kinks, stent eversion, mal-deployment, misaligned deployment) requiring unplanned placement of an additional device within the endovascular stent graft, and
- Successful withdrawal (i.e. successful withdrawal of the delivery system, without need for unanticipated corrective intervention related to withdrawal).

Note: Unanticipated corrective intervention is unplanned implant of a third party device (outside of the Sponsor's available device platform) to treat/exclude the aneurysm.

\*\* Defined as deep vein thrombosis, pulmonary embolism, embolic stroke, limb ischemia in the presence of occlusion or thrombosis within the stent graft.

Additional assessments that will be reported at follow up include:

- Type I, II, III and IV endoleaks and endoleaks of unknown origin
- Stent graft migration > 10 mm (compared to 1-month baseline; assessed at 6-months)

- AAA enlargement > 5 mm (compared to 1-month baseline; assessed at 6-months)
- AAA rupture
- Conversion to open repair
- Secondary interventions\*\*\*

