- AAA-related mortality\*\*\*
- Device-related AEs & SAEs\*\*\*
- Major Adverse Events (MAE)\*\*\*
- Loss of patency
- Stent fracture
- Thromboembolic event (deep vein thrombosis, pulmonary embolism, embolic stroke, limb ischemia)

\*\*\*These assessments will be reported at 12 months in addition to the 12-month Primary Effectiveness endpoints listed above. MAEs and device-related SAEs will be adjudicated by the Clinical Events Committee (CEC) at 1, 6 and 12 months.

MAE is defined as:

- All-cause mortality: any death occurring during the study period, regardless of cause
- Myocardial infarction: the presence of raised levels of one or more cardiac biomarkers in comparison to local laboratory reference ranges
- Stroke (excludes TIA) : a sudden development of neurological deficit due to vascular lesions of the brain such as hemorrhage, embolism, or thrombosis that persists for >24 hours
- Renal failure (excludes renal insufficiency): the need for temporary or permanent dialysis
- Respiratory failure (excludes COPD or pulmonary complications): pneumonia or respiratory failure requiring ventilator support beyond 24 hours post-procedure
- Paralysis (excludes paraparesis): paralysis of the lower extremities inclusive of the lower trunk
- Bowel ischemia: the lack of adequate blood flow to the intestines that requires intensification of medical therapy or surgical/endovascular intervention
- Procedural blood loss ( $\geq 1,000$  mL): estimated blood loss during the index procedure  $\geq 1,000$  mL

---

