In a multi-center AAA clinical trial evaluation of open versus endovascular treatment, Matsumura reports the rates of major adverse events were significantly lower in the endovascular group (14%) than those in the control group (57%). Patients in the endovascular treatment group also experienced less blood loss, a reduction in need for transfusions and a shorter length of hospital stay.

The following outlines morbidities associated with EVAR:

Complication	Range	Average*
All Cardiac (includes myocardial infarction, congestive heart failure, and new cardiac arrhythmias)	0 – 12%	4.9%
Pulmonary (includes pneumonia and pulmonary insufficiency, does not include atelectasis)	0 – 7.7%	2.6%
Renal Failure (chronic and acute)	0 – 6.5%	3.0%
Cerebrovascular Accident	0 – 2.8%	0.3%
Paraplegia or Paraparesis	0 – 0.2%	<0.1%
Access/Deployment Failure	0 – 11%	5.0%
Endoleak	6.5 – 47%	21%
Vascular	0 – 14%	5.1%
Thrombotic/embolic	0.9 – 18%	7.7%
Gastrointestinal	0 – 4.8%	1.4%
Impotence	0%	0%
Hematoma/bleeding/coagulopathy	0 – 24%	5.7%
Wound healing/infection	0 – 14%	3.0%

\*Averages are unweighted from a review of the literature listed in Appendix II.

The literature demonstrates mortality rates for EVAR to be 0–7.5%, with 3.4% as the average. This rate is inflated, to some extent, by the utilization of EVAR in patients who are not candidates for surgical repair because of comorbidities that dramatically increase the risk associated with the surgical procedure. For systemic morbidities (cardiac, pulmonary, renal, cerebrovascular, and gastrointestinal), the rates for EVAR appear to be lower than for surgical repair. The statistical significance of this observation, however, has not been assessed.

Less blood loss, fewer days in the ICU, and a shorter hospitalization is generally reported in patients who undergo EVAR when compared to patients in the surgical control groups. On average, patients treated with EVAR are also able to return to their normal activities quicker than those who receive open surgery.

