### 6.4 *Thrombosis*

Thrombosis is defined as complete occlusion (100%) of the device or native vessel. Thrombosis can be either within the device (device thrombosis) or the native vessel outside the device treatment area (vessel thrombosis). This may be evidenced by: CT, angiography, ultrasound or other imaging modality, or pathological analysis.

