### 6.5 *Stenosis*

Stenosis is defined as narrowing of the blood flow lumen that is less than 100% occlusion. Stenosis can be either within the device (device stenosis) or the native vessel outside the device treatment area (vessel stenosis). This may be evidenced by: CT, angiography, ultrasound or other imaging modality, or pathological analysis.

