## 7.0 ENDPOINTS

### 7.1 *Primary Endpoint*

The primary objective of this study is to evaluate treatment success at 12 months with the Ovation Alto Abdominal Stent Graft System in subjects with AAA.

Treatment success will be a composite endpoint comprised of all of the following:

- Technical success\*;
- Freedom from type I & III endoleak at 12 months, to be assessed by an Independent Core Lab;
- Freedom from stent graft migration > 10 mm at 12 months (compared to 1-month baseline) , to be assessed by an Independent Core Lab;
- Freedom from AAA enlargement > 5mm at 12 months (compared to 1-month baseline);
- Freedom from AAA rupture through 12 months;
- Freedom from conversion to open repair through 12 months;
- Freedom from stent graft stenosis, occlusion, or kink requiring secondary intervention through 12 months;
- Freedom from thromboembolic event attributable to stent graft requiring secondary intervention through 12 months, and:
- Freedom from stent fracture requiring secondary intervention through 12 months

\*Technical Success will be a composite endpoint comprised of all of the following:

- Successful delivery, defined as ability to deliver the implant to the intended location without the need for unanticipated corrective intervention related to delivery, using an adjunctive device outside of the Ovation Alto Abdominal Stent Graft System;
- Successful and accurate deployment, defined as:
  - deployment of the endovascular stent graft in the planned location
  - patency of the endovascular stent graft, absence of device deformations (e.g. kinks, stent eversion, mal-deployment, misaligned deployment) requiring unplanned placement of an additional device within the endovascular stent graft, and;
  - successful withdrawal of the delivery system without the need for unanticipated corrective intervention related to withdrawal

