### ***11.2 Clinical Events Committee***

The Clinical Events Committee (CEC) shall be used to review and adjudicate all device related adverse events (AE) and all serious adverse events (SAE) regardless of the relatedness to the device. The CEC shall also determine which adverse events are considered Major Adverse Events (MAE) for evaluation of the primary (30 days) and secondary (1 year) safety endpoints. The committee shall consist of at least three (3) physicians representing multiple specialties familiar with abdominal aortic aneurysm repair. The CEC will provide their review to the DSMB and shall meet annually, at a minimum.

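### Does Section 7.1 change the primary endpoint by leaving out the definitions of thromboembolic event and corrective intervention that the Protocol Summary and Section 1.0 attach?

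*Combined protocol and SAP*

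**What the plan says.** The primary endpoint is stated three times, in the Protocol Summary, Section 1.0 and Section 7.1.

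- **Section 7.1** gives the component as "Freedom from thromboembolic event attributable to stent graft requiring secondary intervention through 12 months". It has no double asterisk and no footnote.
- **The Protocol Summary and Section 1.0** mark the same component with a double asterisk and define the event in identical words: "Defined as deep vein thrombosis, pulmonary embolism, embolic stroke, limb ischemia in the presence of occlusion or thrombosis within the stent graft".
- **The same two places** carry a Note that limits an unanticipated corrective intervention to the unplanned implant of a third-party device from outside the Sponsor's available platform. Section 7.1 uses the term without the Note.

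Three neighbouring texts bear on the reading. Section 6.4 says "Thrombosis is defined as complete occlusion (100%) of the device or native vessel". Section 6.5 says "Stenosis is defined as narrowing of the blood flow lumen that is less than 100% occlusion". The component just before the thromboembolic one in 7.1 is "Freedom from stent graft stenosis, occlusion, or kink requiring secondary intervention through 12 months".

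The additional assessments in the Summary and Section 1.0 name the same four events without the in-graft condition: "Thromboembolic event (deep vein thrombosis, pulmonary embolism, embolic stroke, limb ischemia". Section 11.2 has the Clinical Events Committee "review and adjudicate all device related adverse events", as well as all serious adverse events.

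**The concern.** Section 7.1 is where a reader looks for the primary endpoint, and on its bare words it is wider than the other two statements. Take limb ischemia caused by an embolus from the graft and treated in the limb artery, with the graft still open. Section 7.1 taken alone scores a failure. The footnoted version scores no event, because limb ischemia there needs occlusion or thrombosis in the graft.

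If Section 6.4's 100% meaning is also carried into the footnote, occlusion and thrombosis become one condition, a fully blocked graft. An embolus from partial thrombus would then not count. The limb-ischemia part would add little, since a blocked graft needing intervention already fails the preceding component.

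The missing Note has a similar effect. An unplanned Sponsor device from outside the Alto System, used to complete delivery, fits 7.1's delivery-failure wording but is not a corrective intervention under the Note.

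At stake is the primary conclusion: in a 60-subject single-arm test, one rescored subject at the boundary decides it.

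**Working it through.** **Plan's figure.** Inputs from Section 8.5: n = 60 evaluable, goal 80%, expected success 92.8%, one-sided exact 95% limit. The rule is the smallest r with P(X ≥ r | 60, 0.80) ≤ 0.05.

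- P(X ≥ 53 | 60, 0.80) = 0.0670, too large.
- P(X ≥ 54 | 60, 0.80) = 0.0308, so r = 54 and six failures are allowed.
- Exact one-sided lower limits: 54/60 gives 0.8121 (meets the goal); 53/60 gives 0.7920 (does not).
- Power = P(X ≥ 54 | 60, 0.928) = 0.8611, matching the stated 86.1%.

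**Scoring under each reading.** All rows are limb ischemia attributable to the graft and needing secondary intervention.

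| State of the graft | 7.1, bare words | 7.1 with the footnote carried over |
|---|---|---|
| Fully occluded | Failure | Failure |
| Partial thrombus, footnote read in ordinary language | Failure | Failure |
| Partial thrombus, footnote read with Section 6.4's 100% meaning | Failure | Not an event |
| No thrombus or occlusion | Failure | Not an event |

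The two columns differ only in the last two rows, and only if the reader declines to carry the footnote into 7.1. The partial-thrombus case also needs the 100% meaning imported. If the narrowing of the graft is itself treated, the stenosis component fails the subject under either reading.

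**Possible size.** The EVAR morbidity table in Section 2.1.3 gives "Thrombotic/embolic" events an average of 7.7% (range 0.9–18%). In 60 subjects that is 60 × 0.077 = 4.6 events of any kind (0.5 to 10.8). The share that is graft-attributable limb ischemia, needs intervention and falls in a disputed row is not in the documents. I assume 5%, 10% and 25%.

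Let d = rate × share.

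- P(at least one disputed subject) = 1 − (1 − d)^60.
- If 92.8% is the footnoted rate, P(conclusions differ) = power(0.928) − power(0.928 − d).
- If 92.8% is the bare 7.1 rate, P(conclusions differ) = power(0.928 + d) − power(0.928).

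| Rate | Share | d | P(≥1 disputed) | Differ, 92.8% = footnoted rate | Differ, 92.8% = bare rate |
|---|---|---|---|---|---|
| 0.9% | 5% | 0.00045 | 2.7% | 0.3% | 0.3% |
| 0.9% | 10% | 0.0009 | 5.3% | 0.6% | 0.6% |
| 0.9% | 25% | 0.00225 | 12.6% | 1.7% | 1.6% |
| 7.7% | 5% | 0.00385 | 20.7% | 2.9% | 2.6% |
| 7.7% | 10% | 0.0077 | 37.1% | 6.1% | 4.9% |
| 7.7% | 25% | 0.01925 | 68.9% | 16.7% | 10.1% |
| 18% | 5% | 0.009 | 41.9% | 7.2% | 5.7% |
| 18% | 10% | 0.018 | 66.4% | 15.5% | 9.7% |
| 18% | 25% | 0.045 | 93.7% | 42.4% | 13.8% |

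A share of zero is equally compatible with the documents and gives zero throughout. The largest entry multiplies the highest rate by the highest assumed share under the harsher anchor.

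**Effect of widening the definition.** Suppose the in-graft condition were dropped everywhere and 92.8% had been derived with it in place. At the 7.7% rate, power would be 0.8611 − 0.0290 = 83.2%, 0.8611 − 0.0605 = 80.1%, or 0.8611 − 0.1670 = 69.4% for the three shares.

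**The case for a change.** The best case for a change has four parts.

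1. Section 7.1 is the operative endpoint section and has no pointer to the footnote, so a reader who starts there could score differently.
2. Neither later authority named in the protocol is told which wording governs. Section 8.3 leaves analysis methods to a separate Statistical Analysis Plan but takes the elements of the composite as given. Section 11.2 gives the Clinical Events Committee the events to adjudicate without saying which definition applies.
3. The footnote drops the limb-ischemia case that this component would add and keeps one that the occlusion component largely covers.
4. Section 8.5 says 92.8% came from applying this study's definitions to the earlier IDE data, without saying which wording was used.

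The first two stand as a drafting gap, and the fourth as something not stated. None of them makes the endpoint ambiguous to a reader of the whole protocol, because only one definition exists.

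The third does not show an error. Overlap between components of a composite does no harm. The limb-ischemia part also keeps a role: if the graft is occluded and the intervention is on the limb artery, the subject may fail here and not under the occlusion component. The third point also depends on importing the 100% meaning from Section 6.4, which makes one of the footnote's two words redundant; Section 6.5 itself uses occlusion for degrees below 100%.

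Deleting the in-graft condition and copying the bare four-event list into 7.1 would not restore 7.1 either. A closed list narrows 7.1's open wording, for example for renal or other visceral emboli, which Section 9.0 recognises as risks.

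**Conclusion.** The omission is real, but it is a gap that analysts would fill sensibly. The Summary and Section 1.0 define the event once, in the same words, for the same component; Section 7.1 gives nothing that competes. Carrying the footnote and the Note into 7.1 is the natural reading and leaves every design number as it is: 60 evaluable subjects, 54 successes needed, 86.1% power.

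Going further and removing the in-graft condition would rewrite a qualifier that the plan states twice. That is a debatable choice of endpoint, not a correction. It could also separate the 92.8% assumption from the definition behind it, with power of 83.2%, 80.1% or 69.4% under the assumed shares at the 7.7% rate.

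The same reasoning covers the Note. Its tension with the delivery wording, which refers to devices outside the Alto System, already exists inside the Summary and Section 1.0, so the omission from 7.1 does not create it.

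This rests on two judgements: that a term defined twice for a component keeps its meaning when the component is repeated, and that no document gives the disputed group a size. The probabilities above show how the result would respond to assumed sizes; they do not estimate one. Repeating the footnote and the Note in 7.1 would be harmless housekeeping, but the plan does not depend on it.

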**PROTOCOL SUMMARY**

Sponsor	TriVascular, Inc. (a wholly owned subsidiary of Endologix, Inc.) [name] [contact]
Protocol Title	Expanding Patient Applicability with PoLymer SEaling OVATion Alto StEnt Graft IDE Study (ELEVATE IDE Study)
Study Description	A prospective clinical evaluation of the effectiveness of the Ovation Alto Abdominal Stent Graft System when used in the treatment of subjects with abdominal aortic aneurysm (AAA)
Study Primary Objective	
To evaluate treatment success at 12 months with the Ovation Alto Abdominal Stent Graft System in subjects with AAA.
 
Treatment success will be defined as:
 
 
• Technical success*;
 
• Freedom from type I & III endoleak at 12 months, to be assessed by an Independent Core Lab;
 
• Freedom from stent graft migration > 10 mm at 12 months (compared to 1-month baseline), to be assessed by an Independent Core Lab;
 
• Freedom from AAA enlargement > 5mm at 12 months (compared to 1-month baseline);
 
• Freedom from AAA rupture through 12 months;
 
• Freedom from conversion to open repair through 12 months;
 
• Freedom from stent graft stenosis, occlusion, or kink requiring secondary intervention through 12 months;
 
• Freedom from thromboembolic event** attributable to stent graft requiring secondary intervention through 12 months, and:
 
• Freedom from stent fracture requiring secondary intervention through 12 months
 
 
*Technical Success will be a composite endpoint comprised of all of the following:
 
 
• Successful delivery, (i.e. ability to deliver the implant to the intended location without the need for unanticipated corrective intervention related to delivery, using an adjunctive device outside of the Ovation Alto Abdominal Stent Graft System);
 
• Successful and accurate deployment, defined as: 
 
○ deployment of the endovascular stent graft in the planned location;
 
○ patency of the endovascular stent graft, absence of device deformations (e.g. kinks, stent eversion, mal-deployment, misaligned deployment) requiring unplanned placement of an additional
 
 
 

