	
device within the endovascular stent graft, and;
 
 
• Successful withdrawal (i.e. successful withdrawal of the delivery system, without the need for unanticipated corrective intervention related to withdrawal)
 
 
Note: Unanticipated corrective intervention is unplanned implant of a third party device (outside of the Sponsor’s available device platform) to treat/exclude the aneurysm.
 
** Defined as deep vein thrombosis, pulmonary embolism, embolic stroke, limb ischemia in the presence of occlusion or thrombosis within the stent graft.

Additional Study Evaluation
	
Additional assessments that will be reported at each follow-up interval include:
 
 
• Type I, II, III and IV endoleaks and endoleaks of unknown origin, to be assessed by an Independent Core Lab
 
• Stent graft migration > 10 mm (compared to 1-month baseline), to be assessed by an Independent Core Lab
 
• AAA enlargement > 5 mm (compared to 1-month baseline), to be assessed by an Independent Core Lab
 
• AAA rupture
 
• Conversion to open repair
 
• Secondary interventions**
 
• AAA-related mortality**
 
• Device-related AEs & SAEs**
 
• Major Adverse Events (MAE)**
 
• Loss of patency
 
• Stent fracture, to be assessed by an Independent Core Lab
 
• Thromboembolic event (deep vein thrombosis, pulmonary embolism, embolic stroke, limb ischemia)
 
 
** MAEs and device-related SAEs will be adjudicated by the Clinical Events Committee (CEC) at 1, 6 and 12 months.
 
MAE is defined as:
 
 
• All-cause mortality
 
• Myocardial infarction
 
• Stroke (excludes TIA)
 
• Renal failure (excludes renal insufficiency)
 
• Respiratory failure (excludes COPD or pulmonary complications)
 
• Paralysis (excludes paraparesis)
 
• Bowel ischemia
 
• Procedural blood loss (≥1,000 cc)
 

Subject Enrollment
	
Patients with AAA will be prospectively enrolled and treated with the Ovation Alto Abdominal Stent Graft System. Treatment

	success at 12 months will be compared to a performance goal of 80%.

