### ***2.1.3 Endovascular Stent Graft Repair***

Since the early 1990's, endovascular aortic repair (EVAR) has evolved into the treatment for AAA at most centers. In 1991, [name] was one of the first to introduce EVAR as a less invasive treatment option for AAA. Since that time, systems for performing endovascular repair of AAA have been developed, improved upon, clinically tested, and approved by FDA for commercial use. The availability of this less invasive technique allows the treatment of patients with multiple comorbidities who may have otherwise been excluded from treatment with open repair due to high surgical risk.

Endovascular grafts, often stented for support, are designed to provide an alternate conduit for blood flow and to exclude the aneurysm from this flow and the associated hemodynamic pressure. Exclusion of the aneurysm significantly reduces its potential for rupture.

Endovascular repair of AAA involves the placement of a stent graft at the location of the aneurysm without the need for performing an open surgical procedure. This technique is less traumatic for the patient by eliminating the need for aortic clamping, thereby reducing the risks associated with decreased blood flow to vital organs and to the lower extremities. Additionally, anesthetic and ventilation time during these procedures are reduced. An endovascular approach also eliminates a significant amount of postoperative pain and discomfort associated with open surgical repair and allows a shorter recovery time for the patient. The length of hospital stay is reduced, which allows patients to more rapidly resume their normal activities of daily living.

During the last 15 years, systems for performing EVAR have been developed, clinically tested, and approved for use. The Ovation platform is approved for commercial use in approximately 40 geographies, including the United States, Europe and Canada. In addition, there are several devices (Excluder, Zenith, AFX, Powerlink, Talent, AneuRx, Endurant, Endurant II, Aorfix and Ancure) approved for use in the United States, with some also approved in other worldwide geographies.

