## 4.0 DEVICE DESCRIPTION

The Ovation Alto Abdominal Stent Graft System is an endovascular device delivered via a low-profile catheter to treat abdominal aortic aneurysms (AAAs). The stent graft is designed to reline the diseased vasculature, providing an endovascular blood conduit for isolating the aneurysm from the high-pressure flow of blood, thereby reducing the risk of rupture. The stent graft is a modular configuration comprised of an aortic body section, iliac limbs, the balloon expandable stent/delivery system as required, as well as iliac extensions as required (Figure 1).

The Ovation Alto Abdominal Stent Graft System includes:

- An Aortic Body Stent Graft and delivery catheter
- Ovation iX Iliac Limb Stent Grafts and delivery catheters\*
- Ovation iX Iliac Extension Stent Grafts and delivery catheters, as required\*
- Balloon Expandable Stent and delivery catheters, as required
- A Fill Kit\*
- An Autoinjector

[figure not shown]
\*Note: These components are currently approved by FDA via PMA P120006.

**Figure 1.** Schematic of Deployed Ovation Alto Abdominal Stent Graft System

The aortic body is comprised of a proximal stent for suprarenal fixation and a low-permeability polytetrafluoroethylene (PTFE) graft. The stent is designed with integral anchors to enable fixation to the aortic wall. For delivery, the stent is in a compressed state within the catheter. When released from the compressed state, the stent expands to engage the vessel wall. The nitinol stent is radiopaque, and radiopaque markers are located adjacent to the graft proximal edge. These radiopaque markers aid placement of the device in its intended location relative to the renal arteries. To seal the proximal end of the graft and to provide support for the aortic body legs into which the iliac limbs are deployed, the graft body contains a network of inflatable rings that are filled with a liquid polymer that solidifies during the deployment procedure. The graft has a fill port that connects the fill network of the graft to the delivery catheter. Figure 2 provides an image of the device with its sealing ring in the aorta.

[figure not shown]

**Figure 2.** Ovation Alto Aortic Body Stent Graft in aorta

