### **8.5 Power Analysis and Sample Size**

The sample size for this study was calculated based on the following assumptions:

- Estimated treatment success at 12 months: 92.8%
- Performance goal: 80%
- Confidence interval estimation: One-sided exact 95% confidence limit
- Statistical power: 86.1%

The power analysis assumptions are based on the following rationales:

- Estimated treatment success at 12 months of 92.8% was derived by retrospectively applying the treatment success definitions in this study to the data observed in Ovation Abdominal Stent Graft System IDE G090239. Given the similarities in device attributes and that no impacts on device effectiveness are anticipated between IDE G090239 and the current study, it is reasonable to assume the same adjusted treatment success rate observed in IDE G090239.
- The performance goal of 80% is a common standard for comparing 12-month effectiveness outcomes in EVAR IDE trials. The pivotal study for the Ovation stent graft utilized the same performance goal. The performance goal may be somewhat more conservative in the current study given the comparatively broader definition of 12-month treatment success.
- A one-sided 95% confidence limit is appropriate since the 12-month treatment success rate with the Ovation Alto would not reasonably be expected to be lower than the 80% performance goal. Therefore, protection against a type I error on that side of the hypothesis is not considered.

Based on these assumptions, 60 evaluable patients are required. In order to account for reasonable attrition, the Sponsor plans to enroll up to 75 patients in this study.

---

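### Does leaving the Note on corrective intervention out of section 7.1 leave the primary endpoint open to two readings?

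*Combined protocol and SAP*

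**What the plan says.** Technical success is a required element of 12-month treatment success (sections 7.1, 8.1 and 8.3). It has delivery, deployment and withdrawal criteria, and the protocol sets them out three times: in the Protocol Summary, in 1.0 and in 7.1.

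- **Section 7.1, withdrawal:** "successful withdrawal of the delivery system without the need for unanticipated corrective intervention related to withdrawal". No definition of the term follows, and section 6.0 does not supply one.
- **Section 1.0, Note:** "Unanticipated corrective intervention is unplanned implant of a third party device (outside of the Sponsor's available device platform) to treat/exclude the aneurysm". The Protocol Summary carries the same Note.
- **Delivery criterion, all three places:** the intervention that counts is one "using an adjunctive device outside of the Ovation Alto Abdominal Stent Graft System".
- **Section 4.0:** the list that begins "The Ovation Alto Abdominal Stent Graft System includes" itemises the system. It takes in the Ovation iX limbs and extensions and the balloon expandable stent. The Sponsor's wider platform, on which the Note relies, is not itemised. Section 2.1.3 says only that "The Ovation platform is approved for commercial use in approximately 40 geographies", and the Summary describes the Sponsor as "a wholly owned subsidiary of Endologix, Inc".
- **Section 8.5:** the origin of the planning rate (92.8%) is given in these words: "derived by retrospectively applying the treatment success definitions in this study to the data observed in Ovation Abdominal Stent Graft System IDE G090239".
- **Section 8.3:** complete analysis methods are left to a prospectively defined Statistical Analysis Plan. No separate plan is in the text available here.

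**The concern.** Section 7.1 is the endpoint section, so a reader may take its wording as the governing one. Taken alone, it seems to differ from the Summary and 1.0 in three ways.

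1. Withdrawal has no device limit in 7.1, so an unplanned repair of a vessel injured on withdrawal could count as a technical failure. Under the Note it could not, because such a repair does not treat or exclude the aneurysm.
2. The delivery criterion draws its line at the Alto System and the Note draws it at the Sponsor's platform. An unplanned Sponsor component from outside the Alto System would fall between the two lines.
3. Section 8.5 does not say which wording produced the 92.8%.

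If this were a real conflict, one patient could be scored a success or a failure on the primary endpoint. In a single-arm study judged against a fixed goal, the reading could then be settled after outcomes were known. The planning rate could also rest on a different reading from the one analysed.

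**Working it through.** **The plan's own figures.** Inputs from section 8.5: goal 80%, expected success 92.8%, one-sided exact 95% limit, 60 evaluable patients, up to 75 enrolled.

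- The smallest passing count c is the least r with P(X ≥ r | n, 0.80) ≤ 0.05. For n = 60, c = 54 (exact error 0.0308).
- Power is P(X ≥ 54 | 60, 0.928) = 0.8611, which matches the stated 86.1%.
- The exact lower limit for x successes is the 5% quantile of Beta(x, n − x + 1). For 54/60 it is 0.8121 and for 53/60 it is 0.7920.
- For n = 75, c = 67 (limit 0.8158; 66/75 gives 0.7999), with power 0.9106.

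**Room for failures.**

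- n = 60: 60 − 54 = 6 allowed and 60 × 0.072 = 4.32 expected, a margin of about 1.7.
- n = 75: 75 − 67 = 8 allowed and 75 × 0.072 = 5.4 expected, a margin of 2.6.

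**What a difference in reading could do.** Assume that 92.8% is the rate under the Note and that exactly k patients are successes under the Note but failures under 7.1 read alone. With X the number of successes under the Note, the verdicts differ when c ≤ X ≤ c + k − 1.

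| k | n = 60 | n = 75 |
|---|---|---|
| 1 | 12% | 8% |
| 2 | 30% | 21% |
| 3 | 50% | 37% |

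These values of k are chosen for illustration. No figure in the documents supports any of them, and k may be 0.

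**Where the readings part.**

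| Event | With the Note | 7.1 without the Note |
|---|---|---|
| Unplanned third-party implant to exclude the aneurysm, related to delivery or withdrawal | Failure | Failure |
| Unplanned additional device inside the graft for a deformation | Failure (deployment) | Failure (deployment) |
| Delivery or withdrawal not achieved; open conversion | Failure | Failure |
| Unplanned Sponsor component from outside the Alto System, at delivery | Not a failure of delivery | Can fail delivery |
| Repair of an access vessel injured on withdrawal | Not a failure of withdrawal | Can fail withdrawal |

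Only the last two rows differ, and both differ for the same reason: whether the Note is carried into 7.1.

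**The two device boundaries.** Within the Summary and 1.0, a delivery failure needs both conditions: an unanticipated corrective intervention as the Note defines it, and a device from outside the Alto System. A Sponsor component is not a third-party device, so it does not meet the first condition and is classified one way only. Anything outside the Sponsor's platform is also outside the Alto System. The Alto wording is therefore redundant there, and it does not contradict the Note.

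**Is 7.1 a rival definition?** The Summary and 1.0 also footnote the meaning of a thromboembolic event, and 7.1 drops that footnote too. The pattern is a list restated without its notes. Nothing in 7.1 gives the term another meaning.

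**The case for a change.** The strongest case for acting is that the endpoint section should be complete in itself. The margin at n = 60 is under two patients. The Core Lab reads imaging and the Clinical Events Committee adjudicates adverse events, but neither is assigned technical success; section 5.5.1.3 records an investigator assessment of delivery, deployment and required interventions. Carrying the Note into 7.1 also leaves the withdrawal criterion with little to catch beyond an outright failure to withdraw. If the wider reading lowered the true success rate by 1, 2 or 3 points, power at n = 60 would fall from 86.1% to 78.1%, 68.7% or 58.6%.

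Part of this stands. The Note is absent from 7.1, the Sponsor's platform is not itemised, and one patient at the 53/54 boundary would reverse the result. The rest carries less weight:

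- Under the Note, a third-party implant needed to restore exclusion after a withdrawal problem still fails the criterion, so the criterion is narrow and not empty. Making it wider would be a different design preference, not the repair of an error.
- The vessel-repair example is arguable even on 7.1 alone. The intervention must be unanticipated, and section 9.0 lists access-site complications and vessel injury among the known risks.
- Section 8.5 says that this study's definitions were applied to the earlier data. Nothing suggests that a different reading was used, and how the earlier study was tabulated cannot be seen.
- Section 8.3 promises a prospective analysis plan, which may already settle the wording. Its absence from the text here does not show that the choice was left open until outcomes were known.

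**Conclusion.** No change to the plan is needed. This is a drafting omission that an analyst fills sensibly: a term defined identically in two sections of one protocol keeps that meaning in a third section that does not redefine it. On that reading every event in the comparison above has a single classification, and the two device boundaries do not conflict. The passing rule of 54/60 and the power of 86.1% are correct as stated.

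The chances of opposite verdicts (12% to 50% at n = 60, 8% to 37% at n = 75) hold only if one to three patients fall in the disputed categories and 7.1 is read in isolation. The documents give no such count, and it may be zero. Repeating the Note in 7.1 at a later revision would be tidy, but it would alter no stated number or decision rule. The conclusion assumes that the separate analysis plan, not seen here, does not redefine the term.
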